Test Up Now Education Program

NCT04304001

Document Date: 1/26/2022

Study Protocol and Statistical Analysis

Study Protocol

The TUNE-UP study is designed as a two-group pretest/posttest pragmatic randomized controlled trial. The study uses the parallel group, two arm superiority trial design with 1:1 allocation ratio. The pragmatic trial aims to test the effectiveness of the intervention in the setting of community health centers. To conduct the intervention trial, 115 participants were randomized at the time of enrollment following completion of the baseline survey. The two experimental arms are: 1) an intervention group which receives the adapted Screen to Save (S2S) educational materials, a tailored brochure for African Americans on colorectal cancer (CRC) screening with input from focus group research, and CHA in-person and cellphone education and counseling supplemented by text messages; and 2) a control group which receives the brochure only. Participants in both study arms received communication from their CHC to receive their stool-based testing kit. The primary outcome is CRC screening by 12-months post-intervention (i.e., receipt of the stool-based test). The intermediary CRC screening outcome is measured at 3-months. Secondary outcomes included CRC knowledge and CRC screening self-efficacy.

Study participants and setting

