African American men and women aged 45 to 64 years were included in the study. Participants were screened for eligibility after contacting the project coordinator according to the following inclusion criteria: (1) 45-64 years of age, (2) self-identify as African American, (3) have a working cellphone, (4) resident of Florida, and (5) not up to date with CRC screening per established screening guidelines (i.e., no stool tests in > 9 months, no colonoscopy within 9 years, and no flexible sigmoidoscopy within 4 years) Exclusion criteria are: previous history of CRC, precancerous colorectal polyps, or co-morbid conditions, such as inflammatory bowel disease or Crohn's disease. The project coordinator reads the consent form and obtains verbal consent from eligible persons interested in participating in the trial. Participants receive the consent form signed by the project coordinator with complete information on the study and university contact information when meeting to complete the baseline survey. Based on recruitment and outreach, research participants are patients of one of two community health centers in the greater Tallahassee, Florida area and primarily reside in two North Florida counties: Leon or Gadsden.

Randomization and blinding

The study used the block randomization method. The trial randomized participants at the individual level, stratified by the two CHC sites, using a 1:1 ratio between intervention and control arms. The randomization algorithm used randomly permuted blocks with random block sizes for the purpose of assigning participants. The random selection of block sizes has the advantage of reducing selection bias. The randomization file was produced in SAS 9.4 by the biostatistician. The Principal Investigator informed the study coordinator of study arm assignment using ID numbers after the participant gave consent to participate in the study and completed the baseline survey. If a participant was assigned to the intervention arm, the study coordinator informed the CHA so the participant could be contacted to complete the intervention arm protocol.

Intervention and control groups

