All statistical analyses were performed using SAS 9.4. First, summary statistics were generated for all variables. Then bivariate analyses were conducted for key variables to compare differences between the intervention and control arms. Proportions calculated from categorical variables were compared using a chi-square test; means obtained continuous variables were compared using two-sample t-test. The multivariate analyses were conducted using the GEE procedure in SAS that implements the generalized estimating equations regression. Analyses were performed using an intent-to-treat approach that includes all participants randomized. Significance tests were two-sided and employed an overall significance level of $\alpha=0.05$. For each arm, the proportion of participants who receive CRC screening by 12 months was computed. The chi-square test was used to compare the two treatment arms for screening receipt. If the proportion of participants receiving CRC screening in the intervention arm is at least 15% higher than that in the control arm, the intervention will be determined to be effective. In addition, since our sample size gets small when participants are stratified by community health center or sex, we will use Fisher's exact test to assess the effect of the intervention. To assess the influence of key covariates (age, income, marital status, education, insurance status) on the primary outcome, logistic regression analysis was employed. In addition, to investigate treatment effects over time (baseline, 3 months, and 12 months), we will estimate hazard ratios by fitting Cox proportional models using time-varying covariates. In these models, the receipt of CRC screening will be regressed at each actual time point on time elapsed since baseline to test for an interaction between time and treatment group. The basic model will be repeated, adjusting for age, income, marital status, education, and any other significant covariates at baseline. To test the proportional hazard assumption, the Kaplan-Meier curve and the Schoenfeld residuals will be used for fixed and time-varying covariates, respectively.

Mediation and moderation analyses will be conducted to determine why and when variables are related, respectively. We will focus on specific mediators to include CRC perceived susceptibility, CRC self-efficacy, and CRC knowledge in the conceptual model.

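### The adjusted Cox model fixes four covariates but lets others in by an undefined significance rule, so its covariate set depends on the data and insurance status may or may not be included

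*Combined protocol and SAP*

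**What the plan says.** All of the relevant text except the sample size and the stratification is in the Statistical analysis section of the combined protocol and SAP.

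- **Primary comparison.** It is unadjusted: "The chi-square test was used to compare the two treatment arms for screening receipt".
- **Logistic model.** It has a closed list of five covariates: "To assess the influence of key covariates (age, income, marital status, education, insurance status) on the primary outcome, logistic regression analysis was employed".
- **Cox model.** It is an additional analysis: "In addition, to investigate treatment effects over time (baseline, 3 months, and 12 months), we will estimate hazard ratios by fitting Cox proportional models". Its adjusted repeat is defined by "The basic model will be repeated, adjusting for age, income, marital status, education, and any other significant covariates at baseline".
- **Baseline comparisons.** The section also reports tests between arms: "Then bivariate analyses were conducted for key variables to compare differences between the intervention and control arms". It does not say that these tests choose covariates.
- **Significance level.** Only one is given: "Significance tests were two-sided and employed an overall significance level of" 0.05. No separate level is set for choosing covariates.

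The Study Protocol section states that "115 participants were randomized at the time of enrollment following completion of the baseline survey". Randomization and blinding says that allocation was "stratified by the two CHC sites, using a 1:1 ratio between intervention and control arms". CHC site is not named in either covariate list.

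**The concern.** The last item in the Cox list does not say what a covariate must be significant for, and both plausible meanings are poor selection rules.

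If it means a difference between arms, randomization makes any such difference a chance event. A 5% test then admits a variable in about 5% of trials whether or not it predicts screening, so a strong predictor outside the four named covariates is left out about 95% of the time. If it means association with screening receipt, the model is chosen from the outcome data that it is then used to analyze.

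At stake is the adjusted hazard ratio. Its covariate set is unknown until the data have been examined, and a different analyst could reach a different model. Insurance status shows the problem within one paragraph: it is fixed in the logistic model, but can reach the Cox model for the same outcome only through the open item.

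**Working it through.** The document gives no power, event count or prognostic strength for this model, so there is no planned figure to reproduce.

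**1. How often an imbalance screen changes the model.** For k independent covariates tested at 5%, the chance of flagging at least one is 1 − 0.95^k.

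- k = 3: 1 − 0.857 = 14.3%
- k = 5: 22.6%
- k = 8: 33.7%
- k = 10: 40.1%

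Beyond the four named Cox covariates, the Statistical analysis section mentions seven others: insurance status, sex, health literacy, family history of cancer, perceived susceptibility, self-efficacy and knowledge. If all seven are measured at baseline and are independent, 1 − 0.95^7 = 30%, and 2^7 = 128 adjusted models are possible.

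**2. What selection does to power.** From the document: 115 participants, 1:1 allocation, two-sided 5% tests, 12-month follow-up, and four named covariates always in the adjusted model. Assumed: baseline hazard 0.045 per month, a constant arm hazard ratio of 2.0, and independent standard normal covariates. There were 1,500 simulated trials per scenario, so the Monte Carlo standard error is about √(0.6 × 0.4/1500) = 1.3 points at 60% power and 1.1 points at 75%.

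- Scenario A: named covariates have log hazard ratio 0.3 per SD; three others have 0.5.
- Scenario B: named covariates have 0.3; one other has 0.3.
- Scenario C: named covariates have 0; three others have 0.5.

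| Power, % | A | B | C |
|---|---|---|---|
| Arm only | 54.5 | 67.8 | 58.5 |
| Four named | 58.9 | 74.6 | 58.3 |
| Four named + others if between-arm p < 0.05 | 59.7 | 74.3 | 59.5 |
| Four named + others if associated with outcome, p < 0.05 | 73.6 | 75.5 | 72.5 |
| Four named + all others, fixed | 76.5 | 76.4 | 74.1 |

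The open item governs only the other covariates, so the right starting point is the four-covariate row.

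- **A.** Available: 76.5 − 58.9 = 17.6 points. The imbalance rule recovers 59.7 − 58.9 = 0.8. The outcome rule recovers 73.6 − 58.9 = 14.7.
- **B.** Available: 76.4 − 74.6 = 1.8 points. The imbalance rule gives 74.3 − 74.6 = −0.3 and the outcome rule 75.5 − 74.6 = 0.9. All are too small to separate from simulation error with confidence.
- **C.** Available: 74.1 − 58.3 = 15.8 points. The imbalance rule recovers 1.2 and the outcome rule 14.2.

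**3. Type I error.** With no arm effect, across the three scenarios, rejection was 4.9–5.7% for arm only, 6.2–6.7% for the four named covariates, 5.8–6.2% with imbalance selection, 6.3–6.6% with outcome selection and 5.7–6.5% with all fixed (standard error about 0.6 points). Neither selection rule stands out from the models with a fixed list.

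**4. Where the gain comes from.** In scenario A, adjusting for everything raises the SD of the estimated log hazard ratio from 0.257 to 0.297, while its mean moves from 0.53 to 0.75. The gain is in power, not in a smaller standard error.

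**The case against.** The strongest reply is that this is a narrow gap in a secondary model. Four covariates enter whatever the data show. The section never ties the between-arm tests to covariate selection. The primary test and the 15% effectiveness rule use raw proportions. The logistic model is meant to describe covariate influence and the Cox model treatment effects over time, so their lists may legitimately differ. All of this stands, and it limits the point.

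A reader might infer more than the document supports:

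- *That adjustment as a whole hangs on a chance imbalance test.* It does not. Only the unnamed covariates do, and the imbalance reading is plausible but not stated.
- *That most of the benefit of adjustment is thrown away.* Measured from the unadjusted model, imbalance selection keeps 59.7 − 54.5 = 5.2 of 76.5 − 54.5 = 22.0 points in scenario A, but 74.3 − 67.8 = 6.5 of 76.4 − 67.8 = 8.6 in B. The answer turns on prognostic strengths that the document does not give.
- *That precision is lost.* In a Cox model, covariate adjustment does not shrink the standard error.
- *That the logistic and Cox results could disagree only because of their covariates.* An odds ratio by 12 months and a hazard ratio can differ even with identical lists.

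The simulation also uses a constant arm effect, whereas the plan tests a time-by-treatment interaction, so its figures are illustrative. None of this supplies a definition for the open item or makes either reading a sound rule.

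**Conclusion.** The point holds as a defect of prespecification in a supporting analysis, and is worth correcting. The adjusted hazard ratio rests on a covariate set that is partly chosen by the data under either reading.

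Under the between-arm reading, the rule adds almost nothing to the four-covariate model: 0.8 of 17.6 available power points in A, none of 1.8 in B and 1.2 of 15.8 in C. Whether the loss is large or trivial depends on how strongly the unnamed covariates predict screening, which is assumed here. Under the outcome reading, most of the power is kept where there is much to gain (A and C), at the price of choosing the model from outcome data.

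A reader might go on to infer that the trial's main conclusion is at risk or that false positives rise. The document and the calculations support neither: the primary chi-square comparison does not use this model, and selection produced no visible type I error inflation.

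**What to change.** In the sentence defining the adjusted Cox model, delete the open last item and close the list as age, income, marital status, education and insurance status, plus CHC site because randomization was stratified by it. Site can be a covariate or a Cox stratum; state which. An imbalance screen would almost never pick site, since the stratified blocks balance it by design. State that between-arm baseline p-values are not used to choose covariates.

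Date the list and say whether outcome data had been seen when it was fixed. This matters because the section reports the baseline comparisons and the logistic model in the past tense and the Cox model in the future tense, so some results may already have been known.

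The cost is a change of wording, a few extra model degrees of freedom (more if the variables have several categories), and possibly a rerun of any adjusted analysis already done.

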To assess the impact of candidate moderators, we will use Cox proportional hazard model and other appropriate survival analysis models to investigate the primary outcome on treatment group, each candidate moderator, and the interaction of treatment and each candidate moderator at each measurement time point.

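### Proportional hazards for fixed covariates is to be tested with Kaplan-Meier curves, which are not a test; baseline covariates, moderators and arm-by-moderator terms are left without a formal check.

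*Combined protocol and SAP*

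**What the plan says.** The Statistical analysis section plans Cox models for screening over baseline, 3 months and 12 months, first unadjusted and then adjusted for age, education, income, marital status and any other baseline variable found significant. On the assumption behind them it says: "To test the proportional hazard assumption, the Kaplan-Meier curve and the Schoenfeld residuals will be used for fixed and time-varying covariates, respectively". It gives no decision rule: no crossing criterion, no log(-log) transformation and no significance level for this check.

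The same paragraph sets up the Cox models "to test for an interaction between time and treatment group".

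The last paragraph of the section adds a second set of Cox models for the moderators, which are named earlier as family history of cancer, health literacy and sex: "we will use Cox proportional hazard model and other appropriate survival analysis models to investigate the primary outcome on treatment group", on each moderator, and on its product with treatment. No check of proportional hazards is stated there.

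**The concern.** The plan divides the two tools by type of covariate, and statistical theory does not support that division. A Kaplan-Meier curve describes one group's experience. It has no null distribution, so it cannot test anything at a stated error rate. It takes no account of other terms in the model. Age (45 to 64 by eligibility) cannot be drawn without cutting it into groups. For an arm-by-moderator term, the curve has no direct reading at all: proportionality of a product term is not something the eye can take from four curves, each holding about 115/4 ≈ 29 people if a two-level moderator splits evenly.

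Schoenfeld residuals are defined for fixed covariates as well as time-varying ones, give a formal test, and come from the fitted, adjusted model. The plan withholds them from the terms where they are most needed.

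At stake is whether single hazard ratios for the baseline covariates, the moderators and the arm-by-moderator terms can be reported as constant over 12 months. The intervention is over within 6 weeks, so effects that change over follow-up are plausible.

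**Working it through.** **Which terms have a formal check?**

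| Term | Named check | Formal? |
|---|---|---|
| Arm, main Cox model | Kaplan-Meier curve, plus time-by-treatment interaction | Yes, through the interaction |
| Age, education, income, marital status | Kaplan-Meier curve | No |
| Family history, health literacy, sex | Kaplan-Meier curve | No |
| Arm by each moderator | Kaplan-Meier curve | No |

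**How informative is a look at the curves at this size?** The documents give no figure to reproduce, so this is an illustration by simulation, for arm only.

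Inputs from the documents: "115 participants were randomized at the time of enrollment following completion of the baseline survey"; "two arm superiority trial design with 1:1 allocation ratio", hence 57 v 58; two-sided 0.05; follow-up to 12 months; and the 15% margin ("is at least 15% higher than that in the control arm"), read as percentage points.

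Assumptions made here: control screening p0 at 12 months of 20, 30, 40 or 50%; piecewise-exponential times with exact dates; no censoring before 12 months; crossing means any sign change in the difference between the two Kaplan-Meier curves.

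Formulas, with p1 = p0 + 0.15:
- H0 = −ln(1 − p0), H1 = −ln(1 − p1), monthly control hazard h = H0/12.
- Proportional hazards: HR = H1/H0.
- Early-only effect: HR in months 0-3 = 1 + (H1 − H0)/(3h), then 1.
- Delayed effect: HR = 1 to month 3, then 1 + (H1 − H0)/(9h).

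Example at p0 = 0.30: H0 = 0.3567, H1 = 0.5978, h = 0.02972. Proportional HR = 0.5978/0.3567 = 1.68. Early-only HR = 1 + 0.2412/0.0892 = 3.70. Delayed HR = 1 + 0.2412/0.2675 = 1.90.

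Results from 4,000 trials per scenario (Monte Carlo standard error at most √(0.25/4000) = 0.8 points). Ranges run over the four control rates.

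| Truth | Curves cross at any time | Curves cross, 3 and 12 months only | Schoenfeld test rejects at 0.05 |
|---|---|---|---|
| Proportional, HR 1 | 78-89% | 33-37% | 5-6% |
| Proportional, HR 1.25 | 80-88% | 31-34% | 5% |
| Proportional, +15 points (HR 1.93 to 1.51) | 69-81% | 19-21% | 5% |
| Proportional, HR 2.5 | 56-59% | 1-9% | 5% |
| Early-only, +15 points | 38-51% | 4-5% | 38-45% |
| Early HR 2.5, then catch-up | 74-79% | 44-49% | 34-72% |
| Delayed, +15 points | 85-92% | 50-54% | 10-11% |
| Early HR 0.5, then above 1, +15 points | 93-98% | 79-87% | 18-33% |
| Early HR 2, then low, about 10 points worse at 12 months | 89-93% | 75-82% | 72-79% |

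Crossing happens in 56-89% of trials when the assumption is true. Whether it happens more or less often when the assumption is false depends on how it fails. The Schoenfeld test holds its error rate at about 5%, but its power ranges from about 10% to 79%.

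**Cost in false alarms.** Four named baseline covariates, three moderators and three products make 10 checks. If they were independent with one test each, the chance of at least one false alarm would be 1 − 0.95^10 = 40%.

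**The case against.** The strongest defence is that arm, the term that matters most, is already tested formally by the time-by-treatment interaction. That stands. The simulation above concerns arm only, so it shows how weak a look at the curves is; it does not measure the gap in the other terms. The primary comparison is a chi-square test of 12-month proportions, which no proportional-hazards check affects. That stands too.

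A reader might infer four stronger points, none of which the documents support:

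- *That at 115 participants the curves cross more often when the assumption holds than when it fails.* This is so for an early effect that fades (75% v 45% at a control rate of 30%). It reverses for delayed or crossing effects (75% v 88-96%).
- *That the planned check gives the wrong verdict.* The plan states no rule for reading the curves, so no verdict can be shown wrong. Crossing is an assumption made here. If only 3- and 12-month status is held, the crossing rates under proportional hazards are much lower (1-37%).
- *That the two tools are simply the wrong way round.* A straight swap would put Kaplan-Meier curves on time-varying covariates, which is no better.
- *That the moderator models assume one constant hazard ratio.* The sentence ends by referring to each measurement occasion and allows other survival models. It is loose, but does not settle the matter.

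It is also fair to say that the formal test has modest power here. That limits what a pass means; it does not make an undefined visual check preferable.

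**Conclusion.** The concern holds in a limited form. The plan names a descriptive display as the test of proportional hazards for fixed covariates and restricts a suitable formal method to time-varying ones. The gap is the baseline covariates in the adjusted Cox model, and the moderators and arm-by-moderator terms in the moderation models. All of these are secondary analyses.

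The crossing figures illustrate that looking for crossings is uninformative at this size. They rest on assumed control rates, hazard shapes, exact dates, no early censoring and an assumed criterion, and should be cited only with those conditions.

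**What to change.** Replace the sentence with:

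> Proportional hazards will be assessed with scaled Schoenfeld residuals for all fixed terms in the Cox models, including moderators and arm-by-moderator terms, supported by log(-log) survival plots for categorical variables; Kaplan-Meier curves are descriptive. If only 3- and 12-month status is held, term-by-period interactions are used instead. Where arm or an arm-by-moderator term departs from proportionality, hazard ratios for 0-3 and 3-12 months are reported.

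No new data are needed. The cost is a little more analysis, including period-specific models where a term fails, and several diagnostic tests that raise the chance of a false alarm. Individual rejections should therefore be read together with the plots. With about 10% power for a delayed effect and 38-45% for an early-only one, the report should also say that a non-significant result does not establish proportionality.

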The complexities of the relationships between the exogenous variables (X) and the endogenous variables (Y) as a function of the mediators will be examined using three separate regression models. We will ensure that the assumptions of continuous measurements (i.e., that all variables are measured on a continuous scale), normality (i.e., normal distribution of all variables), independence (i.e., that there is no correlation of errors from one observation to another observation), and linearity (i.e., evidence linear relationships among the variables) are met. We will assess direct causality and indirect causality using standardized regression coefficients (i.e., betas) to determine the direction and magnitude of the effect of one variable upon the other variable.

We will confirm that the mediators (i.e., CRC perceived susceptibility, CRC self-efficacy, and CRC knowledge) are caused by the exogenous variables X and are also the causes of the endogenous variables Y. We will also determine if X loses its significance when M is included in the model. Specifically, we will perform regression analyses and confirm the significance of the relationship between the exogenous (i.e., independent variable - IV) and endogenous variables (i.e., dependent variable - DV), the exogenous and mediator variable, the mediator and the endogenous variables in the presence of the IV, and lastly, we will confirm the lack of significance (or the meaningful reduction in effect) of the relationship between X and Y in the presence of the mediators.

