Additionally, we will assess the moderator variables (i.e., sex, health literacy, family history of cancer) to determine under what condition (i.e., when) a given predictor X/independent variable (IV) is related to an outcome Y/dependent variable (DV). We will assess whether the moderation effect is enhancing (i.e., that is, increasing the moderator would increase the effect of the predictor on the outcome), buffering (i.e., that is, increasing the moderator would decrease the effect of the predictor on the outcome), or antagonistic (i.e., where increasing the moderator would reverse the effect of the predictor on the outcome). We will apply hierarchical multiple regression to examine the effects of the moderating variable. We will assess the interaction effect between X and M and whether or not such an effect significantly predicts the occurrence of Y. All variables will be standardized to facilitate data interpretation and avoid multicollinearity. We will fit a regression model predicting the outcome from both the predictor and moderator variables. We will check that both the effect of the predictor and the effect of the moderator, as well as the model (R²) are statistically significant. Then, we will fit another regression model that includes the interaction effect of the first model and check for a statistically significant R² change and a statistically significant effect of the interaction term to determine if moderation is occurring (i.e., both are statistically significant).

Mediation analysis allows assessment of each covariate's impact on the primary outcome independent of whether the intervention's effect is significant; thus, adding to scientific understanding of the relevance of each. To examine the mediating effects on the primary outcome of each of the short items scored on a Likert-type scale, we will follow the strategy of Baron and Kenny. We will conclude that the candidate covariate is indeed a mediator of the effects of the intervention if: (1) the treatment group indicator is significant; and (2) the candidate covariate is significant, and the coefficient estimate of the treatment group indicator is smaller in absolute value than its counterpart in analysis.

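### The mediation models require every variable to be continuous and normal, which arm and yes/no screening cannot be, and report effect size as standardized betas that depend on the screening rate

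*Combined protocol and SAP*

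**What the plan says.** The mediation paragraphs of the Statistical analysis section set out three regression models linking exogenous variables X, mediators M and endogenous variables Y. They open with a commitment: "We will ensure that the assumptions of continuous measurements", glossed as "that all variables are measured on a continuous scale", and of normality, glossed as "normal distribution of all variables", will hold, along with independence and linearity. Direct and indirect causal effects are then assessed "using standardized regression coefficients (i.e., betas) to determine the direction and magnitude of the effect". Nothing says what happens if an assumption fails.

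X and Y are generic in those paragraphs. The later paragraph on the Baron and Kenny strategy identifies them: the outcome is the primary outcome, the exposure is the treatment group indicator, and the candidate mediators are "each of the short items scored on a Likert-type scale". The mediators named for the conceptual model are perceived susceptibility, self-efficacy and knowledge. The opening Study Protocol section defines the primary outcome as receipt of the stool-based test within 12 months. The Statistical analysis section treats it as yes/no: "For each arm, the proportion of participants who receive CRC screening by 12 months was computed", with a chi-square test and logistic regression.

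**The concern.** The stated precondition conflicts with the variables it governs. A 1:1 treatment indicator and a screened/not-screened outcome take two values each, so neither can be continuous or normal whatever data are collected. An analyst who follows the text cannot start. One who ignores it finds no outcome model named for mediation: logistic regression and Cox models appear in the section for other purposes, while the betas imply linear regression.

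That choice matters for the plan's own rule, which compares the treatment coefficient with and without the mediator. Linear coefficients can be compared directly. Logistic coefficients can move merely because a predictor of the outcome has been added, so an unspecified model leaves room for different mediation conclusions.

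Separately, a standardized beta into a binary outcome mixes the effect with the standard deviation of that outcome, which is fixed by the overall screening rate. It is a poor answer to the question of how much screening changes.

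**Working it through.** The plan gives no screening rates, expected betas or power for mediation, so there is no figure to reproduce. The check has three parts.

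**1. Can the condition be met?** Arm at 1:1 has two values; its excess kurtosis is (1 − 6 × 0.25)/0.25 = −2, against 0 for a normal variable. Screening has two values at any rate. No data can satisfy the condition for X or Y. Likert-type items are ordinal, which adds to the problem but is not needed for the conclusion.

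**2. How does the beta behave?**
- From the plan: 1:1 allocation, so SD(arm) = √(0.5 × 0.5) = 0.5.
- From the plan: a 15% difference between arms in the effectiveness criterion, taken here as 15 absolute percentage points because the text does not say absolute or relative.
- Assumed: the screening rates p0 (control) and p1 (intervention).

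With m = (p0 + p1)/2,

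beta = (p1 − p0) × 0.5 / √(m(1 − m)).

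| Control vs intervention | m | SD of screening | beta |
|---|---|---|---|
| 5% vs 20% | 0.125 | 0.331 | 0.075/0.331 = 0.227 |
| 15% vs 30% | 0.225 | 0.418 | 0.075/0.418 = 0.180 |
| 25% vs 40% | 0.325 | 0.468 | 0.075/0.468 = 0.160 |
| 40% vs 55% | 0.475 | 0.499 | 0.075/0.499 = 0.150 |

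The relation is not monotone. The beta is lowest at m = 0.5 (0.150 at 42.5% vs 57.5%) and rises again above it: 0.160 at 60% vs 75% and 0.227 at 80% vs 95%.

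**3. Which paths move?** A linear mediation model was simulated with 2,000,000 participants per scenario. Arm shifts the mediator by 0.5 SD, each mediator unit adds 5 points of screening, and the direct effect is 12.5 points. The total effect is 12.5 + 0.5 × 5 = 15 points and the mediated share is 2.5/15 = 0.167.

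| Quantity | Baseline 10% | 40% | 75% |
|---|---|---|---|
| Arm to mediator, beta | 0.243 | 0.242 | 0.242 |
| Mediator to screening, beta | 0.134 | 0.103 | 0.135 |
| Direct arm effect, beta | 0.164 | 0.123 | 0.164 |
| Total effect, beta | 0.197 | 0.148 | 0.197 |
| Indirect effect, standardized | 0.033 | 0.025 | 0.033 |
| Indirect effect, risk difference | 0.025 | 0.025 | 0.025 |
| Mediated share | 0.166 | 0.169 | 0.166 |

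Only paths with screening as the dependent variable move. The arm-to-mediator path and the mediated share do not.

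**The case against.** The best defence is that little depends on the size of the betas. A mediator is declared by significance plus a smaller treatment coefficient once the mediator is in the model. In a linear model, rescaling X and Y changes neither p-values nor whether that coefficient shrinks. This stands: a reader might infer that the betas would produce wrong mediation conclusions, and the documents do not support that.

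Three other inferences also fail.
- **A pathway seeming to weaken between 3 and 12 months.** Mediation is tied to the primary outcome, which is screening by 12 months. The analyses over time are Cox models for treatment and for moderators. No comparison of mediation betas across time is planned.
- **Betas that cannot be related to the 15% criterion.** They can be converted back: risk difference = beta × SD(screening)/0.5, for example 0.227 × 0.331/0.5 = 0.15. The criterion also belongs to the primary arm comparison, not to mediation.
- **Total scores being available for every mediator.** The instruments are not described.

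The fall from 0.227 to 0.150 (34%) joins the ends of an assumed range; the steps between neighbouring rows are 21%, 11% and 6%. Risk differences are not free of the base rate either. With a fixed odds ratio of 2, the difference is 4.5 points at 5% control screening and 17.1 points at 40%. Preferring percentage points is therefore partly a choice of scale, though it is the scale on which the plan judges effectiveness.

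None of this answers the first problem. The condition is written for all variables, is stricter than linear regression needs, and cannot be satisfied.

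**Conclusion.** The point holds as a defect in the written mediation plan. The continuity and normality condition is impossible for arm and screening, there is no fallback, and no outcome model is named for mediation. That conclusion rests only on the documents, reading X and Y as arm and screening, as the Baron and Kenny paragraph does.

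The point about betas is narrower. For an identical 15-point difference they range from about 0.15 to 0.23 across the assumed rates, so they describe magnitude poorly for paths into screening. The size of the shift depends entirely on those assumed rates and on reading 15% as absolute.

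The change should be made, but it concerns a supportive analysis. The primary chi-square comparison is untouched.

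**What to change.** In the mediation text of the Statistical analysis section:

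- Delete the requirement that arm and screening be continuous and normal. Keep residual checks for the mediator models only.
- Name the screening model: a linear probability model with robust standard errors. This keeps the with/without-mediator coefficient comparison valid.
- Report total, direct and indirect effects on screening as risk differences in percentage points, with bootstrap intervals for the indirect effect, in place of standardized betas.
- Where a mediator is a single Likert-type item, do not claim that it is continuous or normal. Use a total score only if the instrument provides one.

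The cost is SAP wording and a modest change to the SAS code, with no new data. The small loss is that effects no longer sit on one unit-free scale.
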